The estimand is described by the following attributes:

- Population: participants with moderate-to-severe AD
- Endpoint: number, percent, and/or IRs for first TEAE of interest
- How to account for intercurrent events:
 - Early Permanent Discontinuation of Study Intervention: TEAEs during the posttreatment follow-up visits will not be considered attributable to the study intervention, and
 - Use of Prohibited or Rescue Medication: TEAEs after the use of prohibited or rescue medication, regardless of relation to AD, will be considered attributable to the study intervention
- Population-level summary: the difference in IRs for TEAEs of interest between participants receiving (rather than assigned to) active study intervention versus placebo, and
- Rationale for estimand: TEAEs during the induction period provide the most direct and clean comparison of safety across ISAs because the ADMP requires each ISA to have an induction treatment period. The posttreatment follow-up period is not included due to potentially notable differences across ISAs including, for example, maintenance treatment periods.

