4.6. Safety Analyses

For safety analyses, p-values will not be included unless specified in the ISA-SAP.

Table 4.1. Baseline and Postbaseline Period Definitions for Overall and Induction Safety Analyses

Analysis Type	Baseline Period	Postbaseline Period
TEAEs (induction safety analyses)	Starts from informed consent date for IMMB to just prior to the time of first dose.	Starts at the time of first dose of the study intervention and ends at the earliest of the following: 
 • Time of discontinuation from ISA • Time of discontinuation from study drug • Time of completing induction treatment period (time of the first dose in the maintenance treatment period, if relevant, or the date of the last visit in the induction treatment period), or • Database cut-off date for ongoing studies
TEAEs (overall safety analyses)	
Randomized in the initial period: Starts from informed consent date for IMMB to just prior to the time of first dose.
 
Assigned to Escape Arm from Placebo (if applicable): From the informed consent date for IMMB to just prior to the time of first dose of active study intervention on the escape arm.
	
For participants randomized to active study intervention in the initial period or assigned to escape arm from placebo: Starts at the time of first dose of the active study intervention and ends at the earliest of the following: 
 • Time of discontinuation from ISA • Time of ISA completion, or • Database cut-off date for ongoing studies 
 
For participants initially randomized to placebo: Starts at the time of first dose and ends at the earliest of the following: 
 • Time of discontinuation from ISA • Time of ISA completion • Time of first dose on the escape arm (if applicable), or • Database cut-off date for ongoing studies 

Analysis Type	Baseline Period	Postbaseline Period

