Laboratory tests and vitals (overall safety analyses)	
Randomized in the initial period: The last available value prior to the first dose of study drug.
 
Assigned to Escape Arm from Placebo (if applicable): The last available value prior to the first dose of active study intervention on the escape arm.
	
For participants randomized to active study intervention in the initial period or assigned to escape arm from placebo: Starts at the time of first dose of the active study intervention and ends at the earliest of the following:
 
 • Time of discontinuation from ISA • Time of ISA completion, or • Database cut-off date for ongoing studies. 
For participants initially randomized to placebo: Starts at the time of first dose and ends at the earliest of the following:
 
 • Time of discontinuation from ISA • Time of ISA completion • Time of first dose on the escape arm (if applicable), or • Database cut-off date for ongoing studies.

Abbreviations: ISA = intervention specific appendix; TEAE = treatment-emergent adverse event.

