Participants with elevated or low values meeting specified levels	
Excludes analytes collected qualitatively.
 
Definitions of low and high values in Tables 59 and 60 from FDA's Standard Safety Tables and Figures Integrated Guide will be used for the numerator^a.
 
Includes participants with at least 1 postbaseline measurement.
 
Maximum baseline is used for elevated assessments and minimum baseline is used for low assessments.
 
See Table 24 from FDA's Standard Safety Tables and Figures Integrated Guide^a.
	Overall Analysis
Listing of abnormal laboratory findings	
Includes laboratory analytes collected quantitatively (high or low during postbaseline using Level 2 definitions; see FDA's Standard Safety Tables and Figures Integrated Guide^a) and qualitatively (abnormal during postbaseline).
 
Includes participant identification, treatment group, laboratory analyte collection day (that is, days from start of study intervention), analyte name, and analyte finding.
	Overall Analysis

Abbreviations: SD = standard deviation; SI = international system of units.

^a CDER/BIRRS 2022.

Scatter plots to support clinical laboratory evaluations

Scatter plots of maximum-by-maximum measurements and minimum-by-minimum measurements will not be created a priori. They may be created if warranted after review of the planned tables and figures, using Figures 6.3 and 6.4 from the Analysis and Displays for Labs white paper (PHUSE 2022) as the model. Analysis Data Model datasets will include variables to enable the creation of scatter plots for use in either an interactive tool or for ad hoc figures.

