4.6.5.2. Vital Signs, Physical Findings, and Other Observations Related to Safety

The definitions for last/maximum/minimum baseline/postbaseline provided in Section 4.6.5.1 also apply to this section.

The planned summaries are provided in [Table 4.4](#). The measurements analyzed for vital signs and physical characteristics include systolic blood pressure, diastolic blood pressure, pulse, weight, and temperature.

Table 4.4. Tables and Figures for Vital Signs and Physical Characteristics

Analysis Type	Analysis Details	Sample
Box plots and Mean/SD plots for observed values by visit	Includes participants who have both a baseline and at least 1 postbaseline measurement from a planned visit. Unplanned measurements will be excluded. Last baseline will be used. No inferential statistics.	Overall Analysis
Box plots and Mean/SD plots for change from baseline values by visit	Includes participants who have both a baseline and at least 1 postbaseline planned measurement. Unplanned measurements will be excluded. Last baseline will be used. No inferential statistics.	Overall Analysis
Participants with elevated or low values meeting specified levels, vital signs	Definitions provided in Tables 31-33 from FDA's September 2022 Standard Safety Tables and Figures Integrated Guide will be used for the numerator ^a . Includes participants with at least 1 postbaseline measurement.	Overall Analysis

Abbreviations: SD = standard deviation.

^a CDER/BIRRS 2022.

Scatter plots to support vital sign evaluations

Scatter plots of maximum-by-maximum measurements and minimum-by-minimum measurements will not be created a priori. They may be created if warranted after review of the planned tables and figures, using Figures 6.3 and 6.4 from the Analysis and Displays for Labs white paper (PHUSE 2022) as the model. Analysis Data Model datasets will include variables to enable the creation of scatter plots for use in either an interactive tool or for ad hoc figures.

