4.6.5.3. Hepatic Safety

Hepatic labs include alanine aminotransferase, aspartate aminotransferase, total bilirubin, direct bilirubin, serum alkaline phosphatase, international normalized ratio, and gamma-glutamyltransferase. When criteria are met for hepatic evaluations, investigators will conduct close monitoring of hepatic symptoms and liver tests, perform a comprehensive evaluation for alternative causes of abnormal liver tests, and complete follow-up hepatic safety eCRFs.

[Table 4.5](#) describes the planned summary tables related to hepatic safety.

Table 4.5. Summary Tables and Figures Related to Hepatic Safety

Analysis	Sample
Abnormal Postbaseline Categories – Hepatic Safety Parameters 
 ALT: The number and percentage of participants with a measurement greater than or equal to 1 time (1X), 3 times (3X), 5 times (5X), 10 times (10X), and 20 times (20X) the performing lab ULN during the treatment period for all participants with a postbaseline value. AST: The number and percentage of participants with a measurement greater than or equal to 1 time (1X), 3 times (3X), 5 times (5X), 10 times (10X), and 20 times (20X) the performing lab ULN during the treatment period for all participants with a postbaseline value. ALP: The number and percentage of participants with a measurement greater than or equal to 2 times (2X), and 3 times (3X) the performing lab ULN during the treatment period will be summarized for all participants with a postbaseline. TBL: The number and percentage of participants with a measurement greater than or equal to 2 times (2X), 5 times (5X), and 8 times (8X) the performing lab ULN during the treatment period will be summarized for all participants with a postbaseline value. DBL: The number and percentage of participants with a measurement greater than or equal to 2 times (2X) and 5 times (5X) the performing lab ULN during the treatment period will be summarized for all participants with a postbaseline value. GGT: The number and percentage of participants with a measurement greater than or equal to 2 times (2X) the performing lab ULN during the treatment period will be summarized for all participants with a postbaseline value. 	Overall Analysis
Hepatocellular Drug-Induced Liver Injury Screening Plot (TBL vs. ALT or AST)	Overall Analysis
Cholestatic Drug-Induced Liver Injury Screening Plot (TBL vs. ALP)	Overall Analysis

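### The master SAP sets no induction window for labs and vital signs, so its threshold counts compare unequal follow-up where placebo participants can escape to active drug

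*SAP*

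**What the plan says.** Table 4.1 (SAP 4.6) is titled for both overall and induction safety analyses. Its first row, "TEAEs (induction safety analyses", closes the TEAE window at the end of induction, and a second row gives TEAEs an overall window. Labs and vital signs have one row only, "Laboratory tests and vitals (overall safety analyses".

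In that row the active window covers this group: "For participants randomized to active study intervention in the initial period or assigned to escape arm from placebo". It runs from the first active dose to ISA discontinuation, ISA completion or data cut-off. The placebo window has the same end points plus one more: "Time of first dose on the escape arm (if applicable), or".

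Three outputs count participants beyond a limit, and all three have Overall Analysis as their sample:

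- Table 4.3, labs: "Participants with elevated or low values meeting specified levels"
- Table 4.4, vital signs: "Participants with elevated or low values meeting specified levels, vital signs"
- Table 4.5, liver tests, for example ALT at multiples of "the performing lab ULN during the treatment period for all participants with a postbaseline value"

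These are counts or percentages. Person-years and incidence rates are offered only for TEAE and infection outputs (SAP 4.6.2, Tables 4.2 and 4.6), and several of those outputs have induction versions.

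In FR01, participants without the required response at Week 16 move to LY3454738 escape therapy, with further escape points later (Protocol 4.1). Placebo is not exempt, and the response criterion is redacted.

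**The concern.** Whether a participant ever crosses a limit depends on how long and how often that participant is measured. Under Table 4.1, placebo escapers stop contributing to placebo at their first escape dose and start contributing to active. LY participants contribute until they complete or leave the ISA. A difference between the arms then mixes length of follow-up with any drug effect.

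SAP 4.6.5.1 uses minimum and maximum summaries to pick out analytes whose extreme values are imbalanced and need a closer look. A window that differs by arm can produce such an imbalance by itself. The cost would be safety review spent on the wrong analytes, or a real difference that is hard to tell from a follow-up artefact. No false test result is at stake, because SAP 4.6 plans no p-values by default.

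**Working it through.** The plan states no figure on this point, so there is none to reproduce. The check sizes the lean when the drug has no effect.

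**Inputs from the documents**
- Planned arms: 96 + 68 + 28 = 192 on LY and 68 on placebo (Protocol 4.1).
- First escape: Week 16 (Protocol 4.1).
- Completer's window: last dose Week 40 (Schedule of Activities, Table 2) plus about 12 weeks (Protocol 4.1), so about Week 52. The treatment period ends at about Week 44 (Protocol 9.3.1).
- Postbaseline chemistry draws: 4 by Week 16, 6 by end of treatment, 8 for a completer. Vital-sign visits: 9, 16 and 18. These are read from schedule columns damaged in extraction.

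**Assumptions**
- Share of placebo escaping at Week 16: e = 25, 50, 75 or 88%. The top value is 100 − 12, from the planning placebo EASI-75 rate of 12% (Protocol 9.5). It is an upper bound for Week 16 escape only if the redacted criterion is no stricter than EASI-75.
- Threshold risk over full follow-up: 10% in every arm. Similar retention; later escapes ignored.

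**Model A, constant hazard.** h = −ln(0.9)/52 = 0.002026 per week and Risk(t) = 1 − exp(−h·t), so Risk(16) = 3.19%, Risk(36) = 7.03% and Risk(52) = 10.00%.
- Placebo = e·Risk(16) + (1 − e)·Risk(52)
- LY with escapers = [192·Risk(52) + 68e·Risk(36)] / (192 + 68e)
- At e = 75%: placebo 0.75 × 3.19 + 0.25 × 10.00 = 4.89%. LY (192 × 10.00 + 51 × 7.03)/243 = 9.38%. Ratio 1.92.

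**Model B, fixed risk per chemistry draw.** p = 1 − 0.9^(1/8) = 1.308%. Risk is 2.60% over 2 draws, 5.13% over 4, 7.60% over 6 and 10.00% over 8.
- Overall window at e = 75%: placebo 0.75 × 5.13 + 0.25 × 10.00 = 6.35%. LY (192 × 10.00 + 51 × 5.13)/243 = 8.98%. Ratio 1.41.
- Treatment period only (liver row) at e = 75%: placebo 0.75 × 5.13 + 0.25 × 7.60 = 5.75%. LY (192 × 7.60 + 51 × 2.60)/243 = 6.55%. Ratio 1.14.

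Placebo % / LY %, with the null ratio:

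| Escape share | Mean placebo window (weeks) | A, overall | B, overall | B, treatment period |
|---|---|---|---|---|
| 25% | 43 | 8.30 / 9.76 = 1.18 | 8.78 / 9.60 = 1.09 | 6.98 / 7.19 = 1.03 |
| 50% | 34 | 6.59 / 9.55 = 1.45 | 7.57 / 9.27 = 1.22 | 6.36 / 6.85 = 1.08 |
| 75% | 25 | 4.89 / 9.38 = 1.92 | 6.35 / 8.98 = 1.41 | 5.75 / 6.55 = 1.14 |
| 88% | 20 | 4.01 / 9.30 = 2.32 | 5.72 / 8.84 = 1.55 | 5.43 / 6.41 = 1.18 |

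Mean placebo window = 16e + 52(1 − e); LY as randomised has 52 weeks. Per-visit vital-sign ratios equal the Model B overall column, because half of a completer's measurements (9 of 18, as 4 of 8) fall by Week 16. The liver row under Model A with T = 44 gives 1.15 to 2.04.

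**Early stopping.** Suppose half of the LY participants and half of the escapers stop near Week 24, while placebo participants who did not escape all continue. Some ratios then fall below 1: the liver row gives 0.94 to 1.07 per draw and 0.89 to 1.54 under constant hazard, and vital signs 0.94 to 1.31. If the remaining placebo participants stop at the same rate, no ratio is below 1: liver 1.01 to 1.08 and 1.11 to 1.64, vital signs 1.06 to 1.35.

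**Common window.** If every arm is counted to Week 16 with similar retention to that point, the null ratio is 1.0.

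**The case against.** The strongest objection is that the deciding document is missing. This is the platform SAP. SAP 4 leaves other safety analyses to the ISA-SAP, SAP 4.6.5 lets the ISA-SAP clarify or add to exactly these outputs, and SAP 3 allows a separate induction safety population. Protocol 9.2 and 9.3.1 also refer to induction safety analyses. This stands as a limit: nobody can say from these documents that FR01 will have no induction lab analysis. It does not remove the point, because SAP 4.6.5 specifies these outputs for all ISAs and none of the cited text commits to a count over equal windows.

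A reader might infer that the SAP contradicts its own reasoning, since 4.4 says "TEAEs during the induction period provide the most direct and clean comparison of safety across ISAs". The documents do not support that. The sentence is about TEAEs and about comparability between ISAs, each of which must have an induction period. It does not address LY against placebo within one ISA, so it serves as an analogy only.

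A reader might also infer that the direction of the lean is unpredictable. The early-stopping check shows that a reversal needs stopping to be concentrated in LY participants and escapers. With similar retention the lean is toward LY.

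Other mitigations are real but partial. By-visit plots compare arms at common visits but do not count participants. The Level 2 lab listing gives the collection day, so those findings could be split at Week 16 by hand; vital signs have no such listing. How baseline abnormality enters the lab count follows an external guide and cannot be seen here. If participants already abnormal at baseline are counted, the lean shrinks: with 10% persistently abnormal, the 1.92 becomes (10 + 0.9 × 9.38)/(10 + 0.9 × 4.89) = 1.28.

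**Conclusion.** The point holds for the master SAP. Applied as written to an ISA with placebo-to-active escape, Table 4.1 makes the lab, vital-sign and liver threshold counts compare unequal follow-up, and no equal-window version is specified. With no drug effect and similar retention the counts lean toward LY. Under the assumed escape shares and a 10% risk, the ratio is about 1.1 to 1.55 per chemistry draw and 1.2 to 2.3 under a constant hazard.

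Labs are seen only at draws, so the per-draw figures are the more apt guide. It would be wrong to read the upper constant-hazard values as an expected doubling. In absolute terms the effect is small: at 75% escape, (8.98 − 6.35)% of 68 is about 1.8 placebo participants for the lab row, and (6.55 − 5.75)% of 68 is about 0.5 for the liver row if it stops at end of treatment. The true size is unknown, because the escape criterion is redacted and the event risk is assumed.

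Separately, Table 4.5 counts values in the treatment period while its sample, the Overall Analysis, runs through posttreatment follow-up. That wording needs reconciling in any case. The change is worth making because it is cheap; the cost of leaving it is misdirected safety review.

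**What to change.** 1. Add an induction row for labs and vital signs to Table 4.1, parallel to the TEAE induction row: first dose to the first maintenance dose or last induction visit, or earlier discontinuation.
2. Add Induction Analysis to the threshold-count rows of Tables 4.3, 4.4 and 4.5, make it the main LY-versus-placebo comparison, and keep the overall counts as descriptive. If the ISA-SAP already does this, say so in the master SAP.
3. In Table 4.5, state whether the count ends with the treatment period or includes posttreatment follow-up, and align the sample label.

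Incidence rates over the overall window are not a substitute. Draws are denser in induction, so with draws placed at Weeks 4, 8, 12, 16, 28, 40, 48 and 52 the null rate ratio under the per-draw model is 0.93, 0.84, 0.73 or 0.66 at 25, 50, 75 or 88% escape. Rates alone would over-correct.

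The cost is SAP wording and three more descriptive outputs to produce and review, all from data already collected.

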4.6.1. Extent of Exposure

Please refer to Section 4.6.1 of the ISA-SAP for the extent of exposure analysis.

4.6.2. Adverse Events

Adverse events (AEs) are recorded in the electronic case report form (eCRF). Each AE will be coded to System Organ Classes (SOC) and Preferred Terms (PT), using the Medical Dictionary for Regulatory Activities (MedDRA) version that is current at the time of the database lock. Severity of AEs is recorded as mild, moderate, or severe.

TEAEs are defined as events that either first occurred or worsened in severity during the postbaseline period defined in [Table 4.1](#). The MedDRA Lowest Level Terms will be used in defining which events are treatment-emergent (TE). The maximum severity for each Lowest Level Term during the baseline period will be used as baseline. TE status in the presence of incomplete data will be determined through the following rules:

- if an AE has missing severity during the baseline period, then the baseline severity will be considered mild for determining TE status
- AEs with missing severity during the postbaseline period will be considered TE regardless of severity during the baseline period, and
- AEs with insufficient data on start date to determine the relevant period (for example, AE start year is the same as the treatment start year, but the AE start month and day are missing) will be considered TE.

For AEs occurring on the first day of the postbaseline period, the day and time of the AE start date will be compared with the dosing day and time. If such a comparison cannot be made due to incomplete day and time information, the AE will be considered TE.

Summaries of TEAE data will at a minimum include

- the number of participants in the safety population of interest
- the number of participants experiencing the event in the safety population of interest, and
- frequency, or percentage, relative to the safety population of interest.

As noted in [Table 4.2](#), some TEAE analyses will also include:

- person-years at-risk during the postbaseline period (years from start of postbaseline period to the first event of interest or the end of the postbaseline period, whichever is first), and
- (exposure-adjusted) IRs and corresponding confidence intervals.

For events that are sex specific, the denominator, computation of percentage, and IR will only include participants of the given sex.

System Organ Class mapping

MedDRA PTs are assigned to a SOC through primary mappings (defined by MedDRA). Thus, MedDRA PTs will appear in only 1 SOC.

The planned summaries for AEs are provided in [Table 4.2](#)**Error! Reference source not found..**

Table 4.2. Tables and Listings Related to Adverse Events

Analysis	Details	Analyses
Overview of AEs	The number and percent of participants with: 
 • At least 1 TEAE • SAE • death, and • permanent discontinuation from study intervention due to an AE. 	Overall and Induction Analyses
TEAEs by PT within SOC	The number of participants, percent of participants, and IR of TEAEs using MedDRA PT nested within SOC. SOCs will be ordered by the difference in IRs between all LY and placebo.	Overall and Induction Analyses
Maximum Severity TEAEs by PT	
The number and percent of participants with TEAEs by maximum severity using MedDRA PT.
 
For each participant and TEAE, the maximum severity for the MedDRA PT is the maximum postbaseline severity observed from all associated LLTs mapping to the MedDRA PT.
 
The maximum severity will be determined based on the nonmissing severities. If all severities are missing for the defined postbaseline period of interest, it will show as missing in the table.
 
Events will be ordered by risk difference (total LY versus placebo) within SOC.
 
SOCS will be listed by risk difference.
	Induction Analysis
TEAEs occurring at $\geq 5\%$ by PT	The number of participants, percent of participants, and IR of TEAEs using MedDRA PT occurring in $\geq 5\%$ before rounding. Events will be ordered by decreasing difference in IRs.	Induction Analysis
Listing of AEs leading to permanent discontinuation of study intervention	Primary AE listed on the disposition form will be used and planned treatment group will be listed.	--
Listing of AEs leading to permanent discontinuation from study	Primary AE listed on the disposition form will be used and planned treatment group will be listed.	--
Listing of SAEs	SAEs resulting in death will be identified through a flag in the listing and planned treatment group will be listed.	--

Abbreviations: AE = adverse event; IR = incidence rate; LLT = Lowest Level Term; LY = Lilly product number; MedDRA = Medical Dictionary for Drug Regulatory Activities; PT = Preferred Term; SAE = serious adverse event; SOC = System Organ Class; TEAE = treatment-emergent adverse event.

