The maintenance period includes an “escape arm” for participants whose EASI response suggests the need for a higher dose. The escape therapy is LY3454738 CCI mg CCI.

A participant will receive this escape therapy under the conditions listed here.

Begin LY3454738 CCI mg CCI as escape therapy...	if the participant...
At Week 16	has not achieved an CCI response at Week 16.
At Weeks CCI	has not achieved an CCI response at Weeks CCI

A participant receiving escape therapy will continue receiving escape therapy through the last dosing visit of the study (Week CCI unless the participant is discontinued from study intervention).

Topical rescue medication in the maintenance period is permitted from Week CCI until the end of the study for participants who do not achieve an CCI response, as described in Section 6.9.1.

Posttreatment follow-up period

All participants are expected to have 2 follow-up visits after the last dosing visit, as listed here.

Condition	First follow-up visit	Second follow-up visit
If the participant did not discontinue study intervention early...	occurs approximately 8 wk after last dosing visit	occurs approximately 12 wk after last dosing visit
If the participant did discontinue study intervention early...	occurs after ED and with an approximately 8-week interval between the last dose and this visit	occurs after ED and with an approximately 12-week interval between the last dose and this visit

Blinding

This study design includes investigator and participant blinding (masking) (Section 6.4). Blinding of the participant's original induction and maintenance treatments will continue until all participants have completed their last posttreatment follow-up visit or have discontinued the study. All blinded assessments and sample collections should be completed before a dose is administered at the dosing visits.

Internal assessment committee

During the study, an IAC will review the safety data in an unblinded fashion, as described in the master IMMB protocol, Appendix 1, Section 10.1.5.

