4.4. Secondary Endpoints/Estimands Analysis

The MP-SAP will focus on two safety analyses: (1) overall safety profile across treatment periods including posttreatment follow-up, and (2) safety profile during induction. The ISA-SAP will define the treatment groups, if relevant, for the overall and induction safety analyses.

Please see Section 4.4 of the relevant ISA-SAP for secondary endpoints and/or estimands for efficacy analyses or ISA-specific safety analyses.

Estimand for overall safety analyses

A secondary clinical question of interest is: what is the difference between active study intervention versus placebo in the number, percent, and/or incidence rates (IRs) of treatment-emergent adverse events (TEAEs) of interest?

The estimand is described by the following attributes:

- Population: participants with moderate-to-severe AD
- Endpoint(s): number, percent, and/or IRs for first TEAEs of interest
- How to account for intercurrent events:
 - Early Permanent Discontinuation of Study Intervention: TEAEs during the posttreatment follow-up will be considered attributable to the study intervention
 - Use of Prohibited or Rescue Medication: TEAEs after the use of prohibited or rescue medication will be considered attributable to the study intervention.

- Assignment to Escape Arm (if applicable): if a participant escapes from placebo to active study intervention, subsequent TEAEs will be attributable to the active study intervention, and
- Assignment to Placebo Withdrawal Arm (if applicable): if a participant is re-randomized from active study intervention to placebo, TEAEs will be considered attributable to the active study intervention until the completion of the study
- Population-level summary: the difference in IRs for TEAEs of interest between participants receiving (rather than assigned to) active study intervention versus placebo, and
- Rationale for estimand:
 - TEAEs of interest for participants receiving active study intervention are considered attributable to study intervention

CCI

- the use of prohibited or rescue medication are potential components of treatment regimens and should therefore be attributable to study intervention.

Secondary estimand for safety during induction period

A secondary clinical question of interest is: what is the difference between the active study intervention versus placebo (or active comparator) in the number, percent, and/or IRs of TEAEs of interest during the induction treatment period?

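### The overall safety comparison uses one pooled incidence rate per group, but escape shortens placebo follow-up, so the comparison is biased unless event rates stay constant over time

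*SAP*

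**What the plan says.** **Statistic.** SAP 4.6.2 defines person-years at risk as "years from start of postbaseline period to the first event of interest or the end of the postbaseline period". It gives no time strata. For the overall safety estimand, SAP 4.4 names as population-level summary "the difference in IRs for TEAEs of interest between participants receiving (rather than assigned to) active study intervention versus placebo". In SAP Table 4.2, the table of treatment-emergent adverse events (TEAEs) by preferred term is produced for both the overall and the induction analysis, and "SOCs will be ordered by the difference in IRs between all LY and placebo".

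**Windows.** In SAP Table 4.1 the active window "Starts at the time of first dose of the active study intervention and ends at the earliest of the following": discontinuation from the intervention-specific appendix (ISA), ISA completion, or data cut-off. For participants first randomised to placebo there is a further end point, "Time of first dose on the escape arm (if applicable), or" cut-off. Placebo participants who escape then enter the active group on a new clock. For participants re-randomised from active to placebo, "TEAEs will be considered attributable to the active study intervention until the completion of the study".

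**Timing.** Protocol 4.1 moves a participant to escape therapy at Week 16 if the participant "has not achieved an CCI response at Week 16". The response level is redacted. The schedule of activities (Table 2) puts the last dose at Week 40, and Protocol 4.1 puts the final visit about 12 weeks after the last dosing visit, so about Week 52.

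**Induction.** SAP 4.4 also defines a separate induction safety estimand and regards it as the cleanest comparison. SAP Table 4.1 applies the same end rules to every group in that analysis.

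**The concern.** A pooled IR is an average hazard, weighted by where the person-time falls. Two such averages are comparable only if the hazard is flat or if both groups' time is spread alike over follow-up. Here the spread differs by design. LY carries a long late denominator, and much of the placebo denominator stops at Week 16. For events that cluster soon after treatment starts, late event-poor time then lowers the LY rate far more than the placebo rate.

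At stake are the stated summary of the overall safety estimand and the SOC order in the overall table. Exposure adjustment is there to correct for unequal follow-up, so a reader is likely to trust the adjusted figure. The SAP neither justifies a constant hazard nor plans a check of it.

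**Working it through.** The documents give no expected event rate or exposure, so there is no planned figure to reproduce. The check computes the IRs expected under the SAP's definitions.

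**Inputs from the documents**
- Planned participants (Protocol 4.1): LY 96 + 68 + 28 = 192; placebo 68.
- LY window: 40 + 12 = 52 weeks. Placebo escapers, in the LY group: 52 - 16 = 36 weeks on a new clock.
- Placebo window: 16 weeks if the participant escapes at Week 16, otherwise 52.

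**Assumptions**
- Escape share f = 0.5 to 0.9, all at Week 16. For orientation, Protocol 9.5 plans 12% EASI-75 on placebo, so f would be 0.88 if the threshold were EASI-75.
- No dropout. Placebo risk 10% over Weeks 0-16.
- Hazard h0 = -ln(0.9)/16 = 0.006585 per week in the first 16 weeks on placebo, and RR x h0 in the first 16 weeks on LY. After that, c x h0 in both groups.

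**Formulas, per participant**
- First 16 weeks at hazard h: S = exp(-16h), events 1 - S, weeks at risk (1 - S)/h.
- A further d weeks at hazard k: events S(1 - exp(-kd)), weeks S(1 - exp(-kd))/k, or Sd if k = 0.
- IR = total events / total weeks x 52.18 x 100, per 100 person-years (PY).

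**How unequal the windows are.** Mean scheduled placebo window = 16f + 52(1 - f): 34.0 weeks at f = 0.5 and 19.6 at f = 0.9, against 52 for participants randomised to LY. The share of placebo time in Weeks 0-16 is 16/34.0 = 47% and 16/19.6 = 82%.

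**Worked case: inert drug, no later events, f = 0.9**
- Weeks at risk: 0.1/0.006585 = 15.19 in the first 16 weeks. A 52-week window gives 15.19 + 0.9 x 36 = 47.59; a 36-week window gives 15.19 + 0.9 x 20 = 33.19.
- Placebo: 61.2 x 15.19 + 6.8 x 47.59 = 1,253 weeks = 24.0 PY; 6.8 events; IR 28.3.
- LY: 192 x 47.59 + 61.2 x 33.19 = 11,168 weeks = 214.0 PY; 253.2 x 0.1 = 25.32 events; IR 11.8.
- Ratio 0.42, although the drug does nothing.

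**Worked case: early hazard doubled, no later events, f = 0.9**
- S = 0.81. Weeks at risk: 0.19/0.01317 = 14.43; 52-week window 43.59; 36-week window 30.63.
- LY: 192 x 43.59 + 61.2 x 30.63 = 10,243 weeks = 196.3 PY; 253.2 x 0.19 = 48.11 events; IR 24.5.
- Ratio 24.5/28.3 = 0.87.
- Benchmark with both groups followed 52 weeks: (0.19/43.59)/(0.10/47.59) = 2.07.

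**All cases, LY/placebo overall IR ratio, f = 0.5 to 0.9**

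| Later hazard vs early | Inert drug | Early hazard doubled | Doubled, equal follow-up |
|---|---|---|---|
| same | 1.00 | 1.37-1.38 | 1.36 |
| half | 0.90-0.74 | 1.39-1.15 | 1.53 |
| quarter | 0.82-0.59 | 1.40-1.02 | 1.70 |
| zero | 0.69-0.42 | 1.43-0.87 | 2.07 |

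With equal follow-up the inert ratio is 1.00 in every row. If the later hazard is instead twice the early one, the same formulas give 1.11-1.40 for an inert drug, so the bias turns against LY.

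**Induction window, same doubling:** h0 x 52.18 x 100 = 34.4 on placebo and 68.7 on LY per 100 PY, ratio 2.0 whatever f is.

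**Sensitivity**
- Leaving placebo escapers out of LY, the zero-later-hazard doubling gives 0.80-1.23 at f = 0.9 to 0.6. The effect is therefore not caused by mixing escapers into LY.
- With 5% risk confined to the first 4 weeks, 30% of LY ending at Week 32 and escapers averaging 26 weeks, an inert drug gives 0.49 (f = 0.88) or 0.79 (f = 0.5), and a doubling gives 1.04 or 1.67. Early ending weakens the bias but does not remove it.

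**The case against.** **The induction analysis covers early harm.** This stands as a limit on the point. The same TEAE table is planned over an equal window, and the table of events at 5% or more and the IRs for infections of interest are planned for induction only. It does not repair the overall summary. An induction ratio of 2 beside an overall ratio near 1 could be misread as a signal that faded.

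**Number and percent sit beside each IR.** True, and for early-only events they still show a doubling. They are not adjusted for follow-up, however, and can mislead the other way. With an inert drug, constant hazard and f = 0.9, the model expects 68.6/253.2 = 27% on LY against 8.1/68 = 12% on placebo.

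**Part of the fall from 2.0 is legitimate averaging.** This stands. An effect confined to 16 weeks should shrink when averaged over 52, so the benchmarks are 1.53, 1.70 and 2.07, not 2.0. If the doubling persists and the later hazard is half, the overall ratio is 1.51-1.77 at f = 0.9 to 0.6, against 2.04 with equal follow-up.

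**The inputs are assumed.** The escape threshold is redacted, and no document shows that events are front-loaded. Discontinuation of escape non-responders (Protocol 7.1.2) shortens some LY windows. The final 12 weeks are also not drug-free: the SAP introduction includes follow-up because drug has not yet washed out. The size is therefore conditional; the mechanism is not.

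**The ISA-SAP may add time-split rates.** It is not among the documents, so this cannot be checked. The master SAP's own stated summary would still need to match.

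**Safety p-values are excluded by default, and SOC order is layout.** Both are true, which limits the consequences.

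**Conclusion.** The point holds as a bias in one comparison that the plan does make: the overall LY-placebo IR difference, and the SOC order that follows from it. With declining event rates the bias favours LY, with rising rates it goes against LY, and with a constant rate there is none. At escape shares of 50-90%, no dropout and 10% early placebo risk, an inert drug shows 0.74-0.90 (later hazard half) or 0.42-0.69 (zero). An early-only doubling shows 1.15-1.39, 1.02-1.40 or 0.87-1.43 for later hazard at half, a quarter or zero, against 1.53, 1.70 and 2.07 with equal follow-up.

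Two stronger readings are not supported. A reader might infer that the plan hides early harm; the induction analysis would show it, so the signal is diluted, and in this grid reversed only when there are no later events and escape is very high. A reader might also infer that most placebo time ends at Week 16; that depends on the redacted threshold and fails at 50% escape, where the share is 47%.

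**What to change.** In SAP 4.4 and Table 4.2:

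1. Report overall person-years, first events and IRs by time since first dose of the column's treatment: 0-16 weeks and after 16 weeks.
2. Base the between-group IR difference and the SOC order on the 0-16 week interval, or on the induction analysis.
3. Label the pooled overall IR difference and the after-16-week comparison as descriptive.

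An interval-stratified (Mantel-Haenszel) difference can be added as support but should not be the sole replacement. Placebo time after Week 16 comes mainly from participants who responded and did not escape, so that stratum compares LY with a selected group.

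The cost is SAP wording and one time-split variable in the safety datasets, with no change to trial conduct. The downside is that placebo rates after Week 16 will be imprecise as well as selected. If the ISA-SAP already has such a split, the master SAP should refer to it.
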